## 2 Rationale

Complex digital data capture systems (those incorporating active symptom monitoring, passive sensing and/or machine learning algorithms) may provide a key to improving outcomes by allowing remote, low-burden mental health monitoring, with personalised intervention strategies delivered when needed. Over the past decade, we have developed, evaluated and deployed DRM for psychosis built on the same digital platform: ClinTouch - EMPOWER (NIHR HTA 2017-2020) built on CareLoop (MRC 2013 - 2016), which in turn built on ClinTouch (MRC 2010 - 2012). ClinTouch comprises a clinically validated smartphone app that tracks symptoms daily. In CareLoop, we showed that this technology could be used for real-time monitoring and can be integrated into health-service systems. In EMPOWER, we expanded the functionality with a relapse risk prediction algorithm and a digitally-enhanced model of care and demonstrated that this is a valid model for reducing relapse in psychosis. Our platform technology, built off a systematic development of trial and development, is safe, feasible, has high concurrent validity with researcher and clinician assessment of symptoms, and is acceptable to both patients and health professionals. Research internationally has confirmed that psychosis patients are generally comfortable with the application of DRM to support self-management.

However, our ability to predict relapse accurately is currently constrained by the limited availability of data in terms of breadth, depth and resolution. Our goal is to recruit a cohort of relapse-prone individuals sufficient in size (breadth: size and variability), collect passively and actively sensed data (depth), with high sampling frequency (resolution). We will use a prospective observational cohort study design to derive and test a personalised risk prediction algorithm to estimate the short-term risk of psychosis relapse. A second goal is to develop an adaptive sampling regimen for maximising engagement and information obtained from digital remote monitoring. This study represents a crucial step for understanding the potential for DRM to detect parameters predictive of relapse. At this stage, the main purpose of the study is to collect data. The study is not intended to prevent or treat psychosis.

### 3 Objectives and Outcome Measures/Endpoints

#### 3.1 Aims

The aims of this study are to collect sufficient data that will enable us to derive and validate:

- i) a risk prediction model that can use actively and passively collected data from DRM to accurately (and dynamically through time) predict an individual's risk of clinical relapse occurring within the next 7 or 28 days;
- ii) an adaptive sampling regimen for maximising engagement and information obtained from DRM.

#### 3.2 Objectives

There are four objectives:

*Objective 1:* To develop a scalable digital platform that incorporates active symptom monitoring (of psychotic and mood/emotion symptoms), and uses sensor-based behavioural, contextual and environmental data gathered from a smartphone and wearable device.

*Objective 2:* To predict psychosis relapse. We will recruit a cohort of relapse-prone individuals with psychosis and collect information described in Objective 1 to determine whether we can develop a risk prediction algorithm of relapse (we will not test the algorithm in this study; rather, we will collect the data to develop the algorithm, ready for testing in a later clinical trial).

*Objective 3:* To examine the utility of passive data. Passively collected data via smartphones and wearable devices could be used both as predictors of relapse and as a way of reducing the burden imposed by ASM. We will evaluate the data quality and acceptability of different wearable devices (smartwatch vs Fitbit comparison) that integrate with the digital data capture platform in order to assess which is the most feasible and acceptable wearable device to use longer term.

*Objective 4:* To develop an adaptive sampling framework. In the future, we aim to develop an integrated digital platform that not only predicts relapse, but also requests information from an individual at the right time and frequency, thereby minimising the burden on the user, while striking the right balance between ASM vs PSM.

#### 3.3 Research questions

The research questions are focused around our two key goals: relapse prediction algorithm and adaptive sampling algorithm:

1. Are there a set of variables that are most predictive of relapse? Are passive and/or active predictors of greatest relevance and for which types of symptoms/outcomes?
2. Can the data collected be used to develop a new prediction algorithm that uses ASM, physiological and behavioural data collected via continuous passive sensing technology, to predict relapse at different time-points (e.g. 7 or 28 days) using a range of advanced analytical methods, with high (and clinically acceptable) specificity and sensitivity?
3. What level of usability, acceptability and adherence to ASM and PSM is required to provide real-time multidimensional indications of clinical state in individuals with psychosis?
4. How does our risk prediction algorithm compare against static risk prediction models (i.e. existing risk prediction models that don't use DRM information)?
5. Is the use of prediction algorithms to support care acceptable to people with lived experience and clinicians?

6. Which statistical methods for adaptive sampling regimens show most promise in maximising engagement with, and information obtained from, digital data collection?
7. Are there 'at risk' periods where engagement might be lost (e.g. a prediction algorithm where stable, low symptom severity leads to sustained disengagement)?

### **3.4 Primary outcomes**

Our primary outcome is clinical relapse, occurring within the next 7 or 28 days.

### **3.5 Secondary outcomes**

Our secondary outcomes are:

- ii) Disengagement with DRM devices
- iii) Acceptability of a wearable device
- iv) Acceptability of DRM and study procedures

### **3.6 Work leading to current study**

We have obtained ethical approval to conduct qualitative interviews in Phase 1 of the research programme (West of Scotland REC 4, IRAS ID 305509). The aim of this study is to inform the DRM platform and our study procedures. Briefly, the Phase 1 qualitative work involves interviewing approx. 60 people with lived experience of psychosis and approx. 40 staff members (or until data saturation is reached) about their views on complex DRM systems and their potential for use in managing severe mental health problems. Specifically, we seek to understand:

- barriers, enablers (and unintended consequences) relevant to the uptake of a DRM system for psychosis and its future integration into existing NHS and/or digital mental healthcare provision infrastructure;
- barriers to people with lived experience of psychosis and staff engaging with digital tools in the context of mental healthcare;
- concerns people with lived experience of psychosis and staff have around remote monitoring, machine learning systems and passive sensing technologies;
- views about the potential for using active symptom monitoring, passive sensing technology and machine learning methods for relapse prediction specifically;
- concerns around data sharing and trust online;
- ethical/governance issues associated with data storage/tracking in a digital health context;
- operability and design features;
- how should data collected via DRM systems be optimally managed, processed and stored;
- what levels of sensitivity and specificity are acceptable to service users and staff? i.e. acceptable levels of efficacy.

To prepare the DRM platform for deployment in the cohort study, we build on our existing ASM platform (i.e., ClinTouch, EMPOWER) to deliver CONNECT. The Background intellectual property (IP) has already been well established by researchers and software engineers based at the University of Manchester. For example, ClinTouch was developed through an MRC funded project (PI: [name]) as smartphone monitoring system to record real-time data on current symptoms, establish the

acceptability of mobile monitoring in psychosis and compare against conventional and gold standard measures of psychiatric symptoms. CareLoop, was also funded by the MRC (PI: [name]) and builds on ClinTouch. EMPOWER (funded by the NIHR HTA; PI [name]) extended the ClinTouch item set to include fear of relapse and contextual items to inform a relapse prevention pathway.

This platform consists of an ASM app operable on both iOS and Android smartphones, a data repository for real-time data collection, and a portal for participant management and reviewing data. The platform is being enhanced to provide tools and computing power for algorithm development and passive data integration (using the open-source Radar-base framework) and a dashboard for participants to view their data. The platform will be stress-tested prior to deployment in the cohort study to ensure it is scalable to the data volumes, responsive and robust to failure. We will undertake usability testing on the near-final (Beta) version of the digital platform through consultation with members of our advisory group and research team to ensure defects are fixed and the platform is accessible, clear, usable and functional prior to deployment in the cohort study. Emphasis in user and usability testing will be on assessing the ease with which test users can navigate the platform and perform simple tasks. Feedback will be reviewed by the research team to optimise the navigation, look and feel and usability of the DRM platform.

## **4 Study Design**

### **4.1 Design**

Prospective, observational (non-randomised, non-interventional) study with an in-built process evaluation and assessment of feasibility and acceptability of wearable devices, using commercially available wearable technology and smartphone sensors, representing no change to the usual care or treatments of participants due to participation. There is no control comparison group, or randomised group allocation.

We aim to recruit 1100 relapse-prone individuals with a schizophrenia spectrum diagnosis. To achieve our objectives, we will recruit one cohort (data will be split into two groups):

- i) Group 1 ( $n = 800$ ): in which we will derive and internally test a personalised relapse risk prediction algorithm using ASM items, passively collected behavioural, environmental and contextual data, integrated using machine learning (see statistical analysis section for details of the methods). We will also develop the adaptive sampling algorithm.
- ii) Group 2 ( $n = 300$ ): in which we will apply and temporally test the risk prediction algorithm and the adaptive sampling algorithm from Group 1. Note the adaptive sampling algorithm will not change the data collection in any way, nor will it be used to monitor, prevent or treat psychosis; we will simply use the data collected to test the algorithm.

This design of derivation/internal validation and subsequent temporal validation is appropriate to assess the algorithm's validity. Group 2 acts as a temporal validation set to test the prediction model and the adaptive sampling model on previously unseen individuals (recruited latest in time).

A future study will examine whether our predictive and adaptive sampling algorithms can improve clinical decision-making on early intervention for psychosis relapse (but this will not be tested in the proposed study).

## 4.2 Study setting

This is a multi-site study, with participant recruitment and data collection occurring across six geographical locations (Manchester, Glasgow, Edinburgh, London, Sussex, and Cardiff). Across these locations, the study involves:

- Nine NHS mental health Trusts/Boards: Greater Manchester Mental Health NHS Foundation Trust; Pennine Care NHS Foundation Trust; South London and Maudsley NHS Foundation Trust; Cardiff and Vale University Health Board; Aneurin Bevan University Health Board; Cwm Taf Morgannwg University Health Board; Sussex Partnership NHS Foundation Trust; Greater Glasgow and Clyde NHS Scotland; NHS Lothian.
- Six Higher Education Institutions (HEIs): University of Manchester; King's College London; Cardiff University; University of Sussex; University of Glasgow; University of Edinburgh.

## 4.3 Eligibility criteria

Participants will be people with lived experience of psychosis on existing caseloads of secondary care mental health teams in NHS Trusts/Health Boards who are:

- I. Adults (16 years and over);
- II. within the past two years have had at least one acute episode of psychosis (including relapse and first episode) leading to an unscheduled episode of acute care, including inpatient admission or acute home treatment / crisis intervention;
- III. received a clinical diagnosis of, or confirmed by the treating clinician to meet the criteria of, schizophrenia spectrum disorder (ICD10 F20 - 29);
- IV. current presentation does not include severe acute symptoms;
- V. in accordance with the Mental Capacity Act, mental capacity will be assumed. If there is any doubt, then a capacity assessment will be carried out by a clinician from the study team or the responsible clinician. Capacity will be recorded on the Referral Form (Appendix N).

Exclusion criteria: Experienced a recent relapse within the previous 12 weeks as confirmed by the treating clinician; non - English speaking.

## 5 Study Procedures

Participants will be asked to wear a wrist-worn device (either a Fitbit or smartwatch) for the study period, during which longitudinal heart rate, accelerometry data, for example, will be prospectively collected. During the same period, standard in-built smartphone sensors will collect for example data on call activity (not the content of calls), (obfuscated rather than exact) location, physical activity, sleep, battery life, light levels. Participants will be prompted via the CONNECT app throughout the week to provide subjective information (rated on a Likert scale using a simple slider in the app) about symptoms, mood and other contextual items. The subjective report provides reliable insight into the variability of participants experiences over time, and has been used in previous studies ( ([name], et al., 2018) (Eisner, et al., 2019) ([name], et al., 2020) (Palmier-Claus, et al., 2012)).

All participants will receive usual multi-disciplinary care. No treatment will be withheld as it would be unethical to restrict the therapeutic options of the clinical teams participating. All routine and additional treatments will be monitored and recorded (from the medical record and in clinical assessments) over the study period.

Participants will be asked to complete, either face-to-face or remote (online or via telephone), multiple visits with a member of the research team (See Section 12.1 for Schedule of Assessments). No research activities will take place prior to informed consent being obtained.

### **5.1 Consent and baseline assessment (approx. 90 minutes)**

Members of the research team will confirm eligibility, obtain informed consent (if not already given) and undertake a Baseline assessment. Key socio-demographic (age, ethnicity, gender, education, relationship status, work status, living situation) and clinical characteristics will be recorded at Baseline.

We will seek consent from participants for access to their medical record throughout the study period to capture key information on relapse and factors including (not limited to) self-harm/suicidal ideation and service contacts (missed appointments, service use, admissions) to examine other important moderators and predictors of relapse. Additional optional consent will be sought to access information held by NHS England/NHS Scotland/NHS Wales and/or their local Integrated Care Board/Health Board, and link this to the information already collected. Access to this information will only be carried out for the study and there will be no further access once the study ends.

### **5.2 Onboarding (approx. 60 minutes)**

All participants will receive an initial 'Onboarding' session (after the Baseline visit) where they will meet with a researcher who will introduce the rationale for using the CONNECT app and wearable device, collaboratively set up, customise and familiarise the participant with the devices (the smartphone and wearable device of their choice), and conduct simple awareness training around digital data capture (including pros / cons / anticipated benefits). Practical information will be provided, including how to switch devices on and off, how to charge devices, and how to respond to alert notifications in the CONNECT app. We will also remind people what data we will not be accessing (e.g. no access to photos, precise location, etc).

The participant will be provided with:

- i. the choice of a smartwatch (Apple watch) or fitness tracker (Fitbit) wearable device (depending on their preference and type of smartphone used);
- ii. an Android smartphone if they do not already own a smartphone, if their smartphone is not compatible with the DRM software platform, or if they would like one. If a participant already owns and uses a DRM compatible smartphone, they will be able to use it.

The researcher will assist the participant in installing the CONNECT app. Each participant's digital literacy skills will be assessed to identify where there are gaps and spend longer training, where needed. At the end of the training session, participants will be asked to start using the wearable and smartphone, and active and passive recording of data will begin (see description of CONNECT app items and passive data we will collect in Section 5.8). Participants will be encouraged to live their life as normal, responding to alerts and notifications when requested.

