*Passive monitoring in psychosis:* Smartphone and wearable device passive sensors have emerged as tools to assess behavioural patterns in a range of populations. Compared to conventional rating scales, social behaviour captured by measures from a smartphone/wearable device can provide a valid, real-world measure of social and behavioural functioning. Sensors in the mobile device that detect movement and surrounding context may indicate sleep disturbance, inactivity, social avoidance or sedentary behaviour. Changes in passive data linked to deterioration in emotional and psychosis symptoms can also be used to identify people for whom an intervention addressing these passive physiological markers may be helpful. As such, PSM tools have been utilised to both reduce burden associated with ASM and gather additional objective, behavioural data.

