### **5.6.2 Payment**

Participants will receive £20 per clinical assessment, and for taking part in a qualitative interview (should they choose) (using vouchers, in cash or via a bank payment) and reimbursement for reasonable travel expenses, if applicable. The amount was decided upon based on NIHR INVOLVE guidelines.

Participants will be provided with a smartphone (if they do not own one or choose to use a study handset) and a wearable device. Data network charges for the study period (up to 12 months) will be paid for, irrespective of whether the participant is given a handset/not (£10/month). The CONNECT platform will be developed to have optimal data usage, relying on WIFI to upload information securely. It is anticipated that participation will not exceed monthly data allowances, however this will be assessed and iterative changes will be made where required.

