### **5.8.2 Passive data collection**

#### *Smartphone sensors*

All modern smartphones have measurement sensors. Data collected passively via the smartphone sensors and a wearable device will be collected via the CONNECT app. These data will be passively collected, requiring minimal or no input from participants. Data collected passively correspond to a range of categories considered putatively relevant to the study, including:

- i. movement sensors: acceleration, gyration, and steps, and obfuscated relative GPS location (relative location to a unknown fixed point only);
- ii. social characteristics: call metadata, SMS metadata, and nearby Bluetooth handsets;
- iii. environmental sensors: ambient light, battery level, magnetic field, and weather conditions;
- iv. user interaction with other applications and their phone (see Figure 3 below).

GPS location data will be anonymised; that is, providing relative location data, not absolute coordinates (preventing identification of an individual's home address or precise geographical location). Relative location collects the relative degrees of latitude and longitude data from GPS and/or using cell tower and WI-FI signals. To ensure participants privacy, the absolute location is converted to a relative location by adding a random number to both the longitude and latitude. The random number added is different for longitude and latitude; it is also different for every participant. This pair of random numbers is created by the app and stored for later use. The pair of random numbers is not available or known by the researchers – it never leaves the participant's phone. No absolute location data is streamed to, or stored on, the server.

Secure software (Matomo and Bugfender) will be used to record user activity within the CONNECT app, as well as collect information to help reproduce and resolve technical issues more effectively and produce technical support. Matomo and Bugfender only monitor use of the CONNECT app; they do not monitor other apps or anything else on the participant's device.

Data transfer from the phone to the data repository is dynamically scheduled according to data volumes, phone in low power mode and availability of Wi-Fi connection.

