##### Participants with Android Phones:

- Will be offered a Fitbit, as it is the only compatible wearable device for Android users.
- Participants who already own a Fitbit may continue using their existing device.

This approach minimises the need for participants to carry two phones and ensures seamless integration of wearable data with their respective smartphones.

Participants who enrolled during the pilot phase or the interim period while awaiting ethical approval for revised study procedures, and are using a Samsung smartwatch, may continue using the Samsung smartwatch for the study duration and keep it, but they will be encouraged to switch to a Fitbit, the only remaining compatible device for Android phones, for the remainder of the study.

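### A study phone is open to anyone who wants one, but the protocol does not say that it records whether the sensed handset is the participant's main phone

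*Protocol*

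**What the plan says.** Section 5.2 (Onboarding) lists three routes to a study phone: owning none, or "if their smartphone is not compatible with the DRM software platform, or if they would like one". The last route is not limited to people who lack a compatible phone. For those who have one, the wording permits and does not require: "If a participant already owns and uses a DRM compatible smartphone, they will be able to use it". Section 5.6.2 (Payment) repeats the offer: "a smartphone (if they do not own one or choose to use a study handset". Participants keep the phone (section 5.4). Data charges are paid whether or not a handset is issued (section 5.6.2).

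Section 5.8.2 (Smartphone sensors) takes movement and relative location from the handset, together with "social characteristics: call metadata, SMS metadata, and nearby Bluetooth handsets" and "user interaction with other applications and their phone". Section 1.4 says that sensors of this kind "may indicate sleep disturbance, inactivity, social avoidance or sedentary behaviour".

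The only mention of two phones is in section 5.8.2.2, under Participants with Android Phones, after the rule that matches the wearable to the person's phone: "This approach minimises the need for participants to carry two phones".

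**The concern.** A phone-derived feature describes behaviour only if the phone is the one the person carries and uses. A second handset left in a drawer, but charged and connected, still sends data: no calls, no messages, one location, little interaction. That resembles the pattern the protocol hopes to detect before relapse. If someone starts with the study phone and drifts back to their own, the record shows apparent withdrawal developing over time.

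These values are present, not missing, so the multiple imputation in section 6.3 does not touch them. Three things are at stake: the weight a model gives to phone features, the risk predicted for people with a second handset, and the answer to objective 3 on the utility of passive data. An analysis plan could not reliably repair this later, because main-phone status that was not asked about during follow-up can be recovered only by recall.

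**Working it through.** **Is there a stated safeguard?** The relevant provisions, side by side:

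- Section 9.1.2 asks for the wrist device to be worn round the clock. No matching instruction covers carrying the study phone, using it as the main phone or moving the SIM to it.
- Section 5.8.1 lets the team contact a participant when a device stops sending data. An idle handset that still sends data need not trigger this.
- Section 5.3 provides weekly, then monthly, contact about technical problems and anomalies. It could bring the matter up but does not say that it asks.
- The assessment schedules (Appendices 1 and 2) show no such item.
- Section 5.8.2 gives wrist-based steps, movement, heart rate and sleep. These partly protect the inactivity and sleep readings. Call, SMS, Bluetooth, location and phone-use features have no such back-up.

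**How large could it be?** The protocol gives no figure to reproduce, so every input here is an assumption. Let one phone feature be N(0,1) in ordinary windows and N(−0.95,1) before relapse, with 3% of windows being events. A fraction f of windows comes from non-main handsets and reads N(−1.5, SD 0.3) whatever the outcome. Shares of 10%, 20% and 30% would be 110, 220 and 330 of 1100 participants.

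*No second handsets.* AUC = Φ(0.95/√2) = Φ(0.672) = 0.749. For 60% sensitivity the cut-off is −0.95 + 0.253 = −0.697, so specificity = Φ(0.697) = 75.7%.

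*With a fraction f.* AUC = (1−f)²·0.749 + f(1−f)·(a+b) + f²·0.5, where
- a = P(event on a main phone reads below a non-event on a second handset) = Φ(−0.55/√1.09) = 0.299
- b = P(event on a second handset reads below a non-event on a main phone) = Φ(1.5/√1.09) = 0.925
- a + b = 1.224

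Results:
- f = 0.1: 0.607 + 0.110 + 0.005 = 0.722
- f = 0.2: 0.479 + 0.196 + 0.020 = 0.695
- f = 0.3: 0.367 + 0.257 + 0.045 = 0.669

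For specificity, the cut-off c solves (1−f)·Φ(c+0.95) + f·Φ((c+1.5)/0.3) = 0.6. At f = 0.1, c = −0.807 and specificity = 1 − (0.9 × 0.210 + 0.1 × 0.990) = 71%. At f = 0.2 and 0.3 it is about 66.5% and 62%. Simulation agrees.

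*Adding one independent feature of AUC 0.75* (also an assumption; a wearable feature, for example), simulated specificity at 60% sensitivity is:

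| Non-main share | Phone feature alone | Two features | Two features, status flagged |
|---|---|---|---|
| 0% | 76% | 86% | – |
| 10% | 71% | 84% | 85% |
| 20% | 66–67% | 82% | 84% |
| 30% | 62% | 81% | 83% |

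The loss with two features is therefore 86 − 84 = 2 to 86 − 81 = 5 points. Flagging returns 1 to 2 of these.

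*Other effects in the same simulation.* The fitted slope for the phone feature shrinks from −0.94 to −0.83, −0.74 and −0.67 at the three shares. Risk in non-main handsets is over-predicted, about twofold at the 10% share and less at higher shares. Flagging avoids both. Imputing the flagged values without outcome information gives AUC 0.722, 0.697 and 0.670, against 0.721, 0.693 and 0.668 with no action, so imputation alone restores almost no discrimination.

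**The case against.** The strongest reply is that case report forms, onboarding materials, the app guide and any analysis plan are not shown, so main-phone status may be asked somewhere, and rules for judging a sensor stream valid normally belong in the analysis plan. That stands as a limit: one can say only that the protocol does not state it. It does not remove the point, because what is offered and what is asked at contacts are protocol procedures, and a derivation rule needs the status to have been collected.

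Three stronger readings are tempting and not supported.

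- A reader might infer from "This approach minimises the need for participants to carry two phones" that participants are known to carry two phones. The sentence describes a mitigation for wearable compatibility and reports no such finding. Paying data charges either way also weakens the incentive to take a second handset.
- A reader might take the single-feature fall in specificity to 62% as the algorithm's. Specificity in section 6.4.2 is that of the whole model, which will combine app answers, wrist data and phone features, with participant random effects or landmarking. Centring within person would remove part of a constant offset, though it could neither recover signal that an unused phone never captured nor correct drift. The drift effect was reasoned and not simulated.
- A reader might conclude that study phones should be withheld from owners of compatible phones. The free choice is a defensible inclusion decision. Restricting it could deter people who do not want sensing on their own phone, against the representativeness aim in section 6.2.1. It would also fall on Group 2, which is recruited last, so the validation group would differ systematically from Group 1.

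**Conclusion.** The point holds in a limited form. The open offer in sections 5.2 and 5.6.2, combined with the features in section 5.8.2 and the interpretation in section 1.4, lets an idle second handset pass as behaviour, and no stated check separates the two. The social features are the most exposed.

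The size is unknown because the documents give no share of second handsets. Under assumed shares of 10% to 30% and a constant reading 1.5 SD low, which is close to a worst case, one phone feature loses about 0.03 to 0.08 of AUC (0.75 to 0.72 and 0.67). A model with one further independent feature loses about 2 to 5 points of specificity. Most of that loss is information the phone never captured. What recording the status chiefly buys is an unattenuated phone effect, risk estimates that are not inflated for people with second handsets, and a fair reading of objective 3. That justifies a cheap addition to data collection and no change to who may have a phone.

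**What to change.** Keep the handset offer as it is.

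1. **Collect.** Add one item at onboarding and at each existing monthly contact: 'Is the phone with the CONNECT app the phone you mainly carry and use?' Ask current participants at their next contact, including from what date the answer applies.
2. **Analyse.** Do not treat phone-derived features (calls, SMS, Bluetooth, location, phone movement, phone use) from non-main periods as observed low activity. Set them to not measured and carry a handset-status indicator in the models; imputation without the indicator is not enough. Keep app answers and wearable data from the same periods.
3. **Report.** Give the utility of passive data (objective 3) with and without the non-main periods, and state the share of participants and follow-up time affected.

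The cost is one case report form item, one derivation rule and some missing phone features for a minority, which count towards the 60% missingness limit in section 6.4.2. For participants already enrolled, earlier periods can be labelled only by recall, so the value of the item falls the later it starts.
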